1.1 – Synopsis (Intervention Groups and Duration) 6.1 – Study Interventions Administered	Added dosing units to the header columns of Table s1 and Table 5	Correction of a typographical error
1.2 – Schema	
 
• Revised schema to add all study timepoints for both treatment groups
 
• Revised footnotes
 
	For clarity and parallel construction
1.3 – Schedule of Activities 8.13 – Health Economics Data or Medical Resource Utilization	Added SF-12 and EQ-5D-5L questionnaires	For internal document consistency as questionnaires were added as exploratory endpoints
1.3 – Schedule of Activities	Added timepoints at Screening for “Mechanical ventilation status” and “Adverse event review and evaluation”	
To ensure AEs are collected after signing of the informed consent form
 
To ensure that mechanical ventilation status is assessed during screening

1.3 – Schedule of Activities	Added timepoint at Day 60 and Day 90 for assessment of concomitant medications and nonpharmacologic treatments and therapies	For clarity

1.3 – Schedule of Activities	Footnote #4: Added sentence that patients who are discontinued from the study will be contacted by telephone on Day 29 to assess their health status	To determine health status (including survival) at Day 29
1.3 – Schedule of Activities	
 
· Updated SoA to indicate that FiO2, SpO2, PaO2 will be assessed daily
 
· Footnote #9: Added sentence that SpO2, PaO2 (if available), and FiO2 should be measured predose for patients randomized to ravulizumab + BSC
 
	
 
· For clarity
 
· To establish baseline values for these parameters
 

1.3 – Schedule of Activities	Footnote #14: Revised to ensure that immunogenicity sampling is not collected postdose	For clarity
	Footnote #14 and #15: Expanded the predose (within 4 hours of the start of infusion) and postdose (within 4 hours after the end of infusion) sampling windows	Given the half-life of the molecule, these expanded windows allow the investigational site staff to collect protocol-specified laboratory samples within a reasonable timeframe.

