6. Confirmation of meningococcal vaccination within the past 5 years prior to dosing for patients randomized to ravulizumab + BSC. If vaccination cannot be confirmed, the patient should receive prophylactic antibiotics prior to initiating ravulizumab treatment and for at least 8 months from the last infusion of ravulizumab. When patients are vaccinated less than 2 weeks prior to treatment with ravulizumab or after initiation of ravulizumab, they should continue antibiotic prophylaxis for at least 2 weeks after meningococcal vaccination.
7. Can be performed within the 3 days prior to Screening or at Screening. Imaging performed as part of the patient's routine clinical care is expected and acceptable for inclusion in this study.
8. Urine or serum pregnancy tests (beta human chorionic gonadotropin) to be performed in all female patients. A negative pregnancy test result is required before administration of ravulizumab.
9. SpO2 to be measured by pulse oximetry. PaO2 to be measured by arterial blood gas, if available. FiO2 to be measured by supplemental oxygen. For patients treated with ravulizumab, SpO2, PaO2 (if available), and FiO2 should be measured predose on Day 1. The highest daily measurement of oxygen pressure or saturation on the lowest inspired supplemental oxygen level will be recorded in the CRF/eCRF.
10. Complete or abbreviated physical examination is to be performed at the timepoints indicated in the SoA. A complete physical examination will include, at a minimum, assessments of the following organs/body systems: skin, head, ears, eyes, nose, throat, neck, lymph nodes, chest, heart, abdomen, extremities, and musculoskeletal. An abbreviated physical examination consists of at least an evaluation of the respiratory and cardiovascular systems. Clinically significant abnormalities or findings will be recorded in the AE CRF/eCRF.
11. Vital sign measurements should include systolic and diastolic BP (millimeters of mercury [mm Hg]), heart rate (beats/minute), respiratory rate (breaths/minute), and temperature (degrees Celsius [°C] or degrees Fahrenheit [°F]). These measurements will be taken predose on dosing days.

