7.2. Efficacy Analyses

Efficacy analyses will be performed on the ITT population and the PPS will be used for sensitivity analyses. Baseline is defined as the last available assessment on or before Day 1 for all patients. By-patient listings of all efficacy data will be produced.

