7.2.2. Secondary Analyses

A closed testing procedure will be applied to control the type I error for the analyses of the primary and secondary endpoints at Day 29. If the primary endpoint is statistically significant in favor of ravulizumab, the secondary endpoints will be evaluated according to the following rank order:

1. Number of days free of mechanical ventilation at Day 29,
2. Duration of ICU stay at Day 29,
3. Change from baseline in SOFA score at Day 29,
4. Change from baseline in SpO₂/FiO₂ at Day 29,
5. Duration of hospitalization at Day 29.

The hypothesis testing will proceed from highest rank (#1) the number of days free of mechanical ventilation at Day 29 to the lowest rank (#5) duration of hospitalization at Day 29, and if statistical significance is not achieved at an endpoint ($p \geq 0.05$), then endpoints of lower rank will not be considered to be statistically significant. Confidence intervals and p-values will be presented for all secondary efficacy endpoints for descriptive purposes, regardless of the outcome of the closed testing procedure.

An additional secondary endpoint will be assessed beyond Day 29 regardless of the results of the closed testing procedure: Survival (based on all-cause mortality) at Day 60 and Day 90.

The PPS will be used in a sensitivity analysis for all secondary efficacy endpoints.

7.2.2.1. Number of Days Free of Mechanical Ventilation at Day 29

The number of days free of mechanical ventilation at Day 29 will be summarized by treatment group for all patients and by mortality. The number of days free of mechanical ventilation at Day 29 will be compared between treatment groups using an analysis of covariance (ANCOVA), adjusting for age and the randomization stratification factor, among survivors (ie, the number of days alive and free of mechanical ventilation).

Missing data will be imputed using a multiple imputation approach assuming the data are MAR and using a regression model with covariates for treatment group, the randomization stratification factor, age, sex and presence of a pre-existing condition at baseline (diabetes mellitus, obesity, respiratory condition, and/or coronary artery disease). Sensitivity analyses will include:

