Changes in SpO₂/FiO₂ will be also be analyzed using a REML-based repeated measures approach (i.e. MMRM, [Mallinckrodt, 2008](#)) and all available longitudinal data. The model will include fixed effects for baseline SpO₂/FiO₂, age, randomization stratification factor, treatment group indicator, study day (Day 5, 10, 15, 22, 29), and study day by treatment group interaction. An unstructured covariance structure will be used to model the within patient errors. If this analysis fails to converge, the following structures will be tested and the final covariance structure will be determined by Akaike's information criterion (AIC): first-order autoregressive, compound symmetry, and Toeplitz. The Kenward-Roger approximation will be used to estimate denominator degrees of freedom. The daily post-baseline SpO₂/FiO₂ scores will be mapped to study day as described in [Appendix 9.4.6](#). For patients who die, remaining values up to Day 29 will be imputed as a score of 0, the worst possible value.

A sensitivity analysis will be performed using a control-based MNAR mechanism for the missing data as described for change from baseline in SOFA score at Day 29.

This analysis will be repeated for changes in PaO₂/FiO₂, where available, as a sensitivity analysis.

7.2.2.5. Duration of Hospitalization at Day 29

Duration of hospitalization at Day 29 will be analyzed in a similar manner as duration of ICU stay (ie, the number of days alive and not hospitalized). Missing data will be handled as described for number of days free of mechanical ventilation at Day 29. The proportion of patients discharged from the hospital will also be summarized and compared between the 2 treatment groups in a similar manner as the primary analysis of the primary endpoint.

7.2.2.6. Survival at Day 60 and Day 90

Survival (based on all-cause mortality) at Day 60 and Day 90 will be estimated using the KM method and compared using a log-rank test stratified by intubated or not intubated on Day 1. Hazard ratio and risk reduction will be summarized from a Cox proportional hazards model stratified by intubated or not intubated on Day 1. Confidence intervals (95%) will be presented for the survival estimates at Day 60 and Day 90 based on the complementary log-log transformation. KM curves for both treatment groups will be produced.

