9.4.2. Definition of Baseline Values

Baseline is defined as the last available assessment on or before Day 1 for all patients. Day 1 will be defined as the date of the first infusion of ravulizumab for patients randomized and dosed with ravulizumab and as the later of the date of randomization or the date of Day 1 visit for patients randomized but not dosed with ravulizumab.

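### Footnote 9 and the SAP do not fix one Day 1 SpO2/FiO2 baseline for both arms: predose timing is set for ravulizumab only, the day's best is what is recorded, and baseline has no clock time

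*Protocol*

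**What the plan says.** Footnote 9 to Table 1 (Protocol 1.3) has two sentences that bear on the Day 1 value.

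- The first applies to patients treated with ravulizumab: SpO2, PaO2 if available, and "FiO 2 should be measured predose on Day 1". No matching time limit is set for BSC alone. The Amendment 3 summary of changes gives the purpose as "To establish baseline values for these parameters"; I cite it for intent only.
- The second reads "The highest daily measurement of oxygen pressure or saturation on the lowest inspired supplemental oxygen level will be recorded in the CRF/eCRF". It is restricted neither to an arm nor to a day.

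SAP 7.2 states "Baseline is defined as the last available assessment on or before Day 1 for all patients", and SAP 9.4.2 repeats it. Neither gives a clock time or says which of several Day 1 values counts. Day 1 is the first infusion date for dosed patients and "the later of the date of randomization or the date of Day 1 visit for patients randomized but not dosed with ravulizumab".

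SAP 7.2.2 places the endpoint fourth of five in the fixed sequence: "4. Change from baseline in SpO₂/FiO₂ at Day 29". If an endpoint fails, "then endpoints of lower rank will not be considered to be statistically significant", but confidence intervals and p-values are presented for all secondary endpoints. The analysis (SAP 7.2.2.4) is an MMRM on change: "The model will include fixed effects for baseline SpO₂/FiO₂, age, randomization stratification factor, treatment group indicator", with visit and its interaction with treatment. The code in SAP 9.5.2.2.2 has one baseline slope shared by all visits. Deaths are scored 0. Post-baseline values follow one rule in both arms (SAP 9.4.6).

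**The concern.** A change-from-baseline comparison needs a baseline collected in the same way in both arms and before treatment can act. Here one arm has a timing instruction that the other lacks, in an open-label trial, and the SAP's single definition cannot undo a difference created when the value is recorded. If the arms do differ, the best of a day's readings cannot lie below any one reading from that day, so the gap has a known direction: the BSC baseline is higher and the BSC change smaller. At stake are the rank 4 test, the descriptive change summaries (SAP 7.2.2.4) and the baseline oxygenation table (SAP 7.1.3.2). The primary endpoint and the duration endpoints at ranks 1, 2 and 5 do not use this baseline.

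**Working it through.** **Step 1. What the text permits.**

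| Reading of footnote 9 | Ravulizumab Day 1 value | BSC Day 1 value | Arm difference under no effect |
|---|---|---|---|
| Predose value is the baseline | One predose reading, or the best of several | Best of the day, possibly after randomisation | BSC higher |
| Daily best recorded for everyone | Best of the day, possibly after dosing | Best of the day, possibly after randomisation | About zero |

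**Step 2. Plan figures.** The documents give no SD, effect or power for SpO2/FiO2. The only planning figure used here is the primary-endpoint sample size. It reproduces: 60% vs 80%, 2:1, 1-sided 0.025 and 90% power need 240 patients in a fixed design, and 162/81 (the planned 243) gives 90.4%.

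**Step 3. Bias under the first reading.** Let s be the within-day SD, k the number of readings and b the slope of the follow-up value on measured baseline.

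- BSC baseline inflation: d = E[max of k standard normals] × s, with E[max] = 1.03 for k = 4, 1.629 for k = 12 and 1.947 for k = 24 (independent readings).
- Unadjusted difference in change: d, favouring ravulizumab.
- Adjusted difference: change has slope b − 1 on baseline, and the arm difference in measured baseline is −d. So the adjusted difference is d − (b − 1)(−d) = b × d.
- Standard error, single-visit approximation with 162/81: SD × √(1/162 + 1/81) = 0.136 × SD, which is 13.6 for SD 100 and 20.4 for SD 150.
- With z = b × d / SE, 2-sided rejection under no effect is P(Z > 1.96 − z) + P(Z < −1.96 − z).

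All values of s, k, b and SD are assumptions:

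| s | k | d | b | Day 29 SD | b × d | In SEs | Rejection |
|---|---|---|---|---|---|---|---|
| 10 | 4 | 10.3 | 0.2 | 150 | 2.1 | 0.10 | 5.1% |
| 20 | 4 | 20.6 | 0.2 | 150 | 4.1 | 0.20 | 5.5% |
| 20 | 12 | 32.6 | 0.5 | 100 | 16.3 | 1.20 | 22% |
| 40 | 4 | 41.2 | 0.5 | 150 | 20.6 | 1.01 | 17% |
| 40 | 12 | 65.2 | 0.5 | 100 | 32.6 | 2.39 | 67% |

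**Step 4. Deaths scored 0.** If poor baseline oxygenation predicts death, that scoring raises b. Null simulations used 180/90 patients, about 70% survival, single-visit ANCOVA, within-day SD 10 to 20, best of 4 to 24 readings, and 1,500 trials per setting.

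- Survival unrelated to baseline: b about 0.2. Two separate runs gave 1.6 to 9 units and rejection of 4.7% to 8%. The formula gives 0.2 × 10.3 = 2.1 to 0.2 × 1.947 × 20 = 7.8.
- Survival odds ratio 1.5 per baseline SD: b about 0.6, 7 to 25 units (0.3 to 1.1 SE), rejection 6% to 21%.
- Odds ratio 2: b about 0.9, 9 to 33 units (0.4 to 1.6 SE), rejection 7% to 33%.

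**Step 5. Repeated-measures check.** A model with one common baseline slope was run with 162/81 patients, 1,500 null trials per setting, no deaths and strong tracking over time (fitted b 0.53 to 0.76). With different Day 1 rules by arm, the adjusted bias was 8 to 34 units, always favouring ravulizumab, and rejection was 15% to 97%. These rejection rates are high because that setting combines a steep slope with small residual variance. With the same best-of-day rule in both arms, the bias was −0.3 to +0.2 and rejection 3% to 6%.

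**The case against.** A reader might infer that the plan makes the BSC baseline too high and so biases rank 4 towards ravulizumab. The documents do not establish that. The predose sentence says when values are measured; the next says which value is recorded, and it exempts no arm and no day. Read literally, both arms record the daily best and the between-arm bias is about zero. The amendment rationale shows intent but does not switch off the recording rule. This stands: the asymmetry is the likely reading, not a stated rule.

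Four further points limit the size.

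- Nothing restricts ravulizumab patients to one predose reading. The best of several would narrow the gap.
- Baseline is a covariate, so only b × d reaches the test. If b is 0, nothing does.
- Readings within a day are correlated. With equal correlation of 0.7, the inflation shrinks by √(1 − 0.7) = 0.55. A simulation with survival rising about 11 percentage points per baseline SD fell from 8.5–29.5 units to 4.3–15.6.
- A false confirmatory claim at rank 4 also needs the primary and ranks 1 to 3 to succeed first.

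All four are correct. They reduce the consequence but do not settle which value is the baseline. The literal reading has its own cost: a ravulizumab baseline that may post-date dosing defeats the purpose of asking for a predose measurement.

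**Conclusion.** The point holds as an unresolved baseline definition with a conditional bias. As written, the rank 4 baseline is either collected differently by arm or is a best-of-day value that can post-date dosing or randomisation.

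On the first reading, unadjusted change favours ravulizumab by the whole inflation (10 to 65 units for the inputs in step 3). The adjusted estimate favours it by slope × inflation, from about 2 units (0.1 SE) to more than 1 SE. The direction is fixed whenever the slope is positive. The size depends on within-day variability, the number and correlation of readings, and how strongly baseline predicts the Day 29 value and death, none of which the documents give. No single figure within the range should be quoted as the bias.

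On the second reading the arm bias is about zero and the remaining fault is a baseline that is not reliably pre-treatment. Neither reading affects the primary endpoint or the sample size. The correction is worth making because rank 4 results will be reported whatever happens above it in the sequence.

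**What to change.** Reconcile the two sentences of footnote 9, and amend SAP 9.4.2 (with SAP 7.2 to match) so that baseline SpO2/FiO2 and PaO2/FiO2 in both arms is the last paired reading before randomisation, recorded once with its clock time. Apply the daily-best rule only after Day 1.

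Where that reading is missing, state one rule that is identical in both arms and does not depend on a value from before Day 1. Screening and Day 1 may fall on the same day (Protocol 4.1), so an earlier daily value may not exist.

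The cost is a footnote change, a matching SAP definition and one time-stamped entry of a bedside measurement. The downside is a single-reading baseline that is slightly noisier than a daily best. It changes neither the sample size nor patient care.

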## 2. INTRODUCTION

### 2.1. Study Rationale

ULTOMIRIS® (ravulizumab), an effective and widely studied terminal complement inhibitor with a well-established safety profile, is proposed for the treatment of patients who have a confirmed diagnosis of severe acute respiratory syndrome coronavirus 2 (SARS-CoV-2) infection with a clinical presentation consistent with Coronavirus Disease 2019 (COVID-19) severe pneumonia, acute lung injury, or acute respiratory distress syndrome (ARDS). Ravulizumab produces immediate, complete, and sustained inhibition of complement component 5 (C5)-mediated terminal complement activity. Treatment with ravulizumab could decrease COVID-19 induced lung injury (ie, improve clinical outcomes in patients with COVID-19 severe pneumonia, acute lung injury, or ARDS).

### 2.2. Background

The novel SARS-CoV-2 is a beta-coronavirus identified as the causative agent in COVID-19 ([CDC, COVID 19 Situation Summary](#)). Clinical manifestations of COVID-19 range from mild flu-like symptoms (eg, low grade fever, cough, fatigue) to ARDS, respiratory failure, multiple organ failure, and eventual death. An accelerating incidence of SARS-CoV-2 infections have been reported for patients who present with severe pneumonia, acute lung injury, or ARDS.

Emerging epidemiologic data indicate that approximately 30 - 50% of patients with COVID-19 may require hospitalization, approximately 10% may be admitted to critical care units, and 2.5% or more may die of multiorgan failure, especially those individuals who are older or have other comorbidities. For hospitalized patients, the World Health Organization (WHO) has issued recommendations on disease management and therapeutic regimens ([WHO, 2020](#)). Aside from supportive care, no therapeutic regimens have been proven effective in reducing either the human-to-human transmission of the infection or its associated fatalities. Mortality in those with critical illness has been reported as > 50%; therefore, implementation of proven critical care interventions such as lung protective ventilation is recommended by WHO.

#### 2.2.1. Nonclinical Evidence Supporting the Role of Complement in COVID-19

Acute respiratory distress syndrome is a constellation of immune-mediated pathologies that are observed in severe cases of coronavirus infection ([Hammerschmidt, 1980](#)). This pattern was observed in 2002 with the emergence of severe acute respiratory syndrome-coronavirus (SARS-CoV), and in 2012 when a related coronavirus, Middle East respiratory syndrome coronavirus (MERS-CoV) was identified ([Rota, 2003](#), [Zaki, 2012](#)). Complement activation and complement component 5a (C5a; the proinflammatory anaphylatoxin) are involved in multiple mechanisms in the development of acute lung disease induced by pathogenic viruses ([Wang, 2015](#)). Emerging evidence suggests that activation of the complement system is involved in the pathogenesis of coronavirus (CoV)-related ARDS, and that a C5 inhibitor may be an effective therapeutic in CoV-mediated disease ([Gralinski, 2018](#)).

The complement system is a part of the immune system that enhances the ability of antibodies and phagocytic cells to clear pathogens and damaged cells. It is made up of more than 30 plasma

proteins that opsonize pathogens and induce a series of inflammatory responses to help fight infection. The complement system has key roles in innate and adaptive immune responses, but when hyperactivated can lead to tissue injury. Within the complement system there are 3 pathways (classical, lectin, and alternative) that lead to cleavage of C5 and formation of the membrane attack complex, or terminal complement pathway.

Preclinical data have demonstrated a role for complement activation in CoV-mediated disease. Gralinski evaluated activation of the complement system in a mouse model of CoV. The C57BL/6J mice were infected with mouse-adapted SARS-CoV which resulted in high-titer virus replication within the lung, induction of inflammatory cytokines and chemokines, and immune cell infiltration within the lung. Complement activation was measured by detection of complement pathway component cleavage products. Complement protein 3 activation products were detected in SARS-CoV MA15-infected mice, but not in control mice, as early as 1 day post-infection. Complement protein 3 deposition was observed in the lungs of infected wildtype mice on Day 2 and Day 4 post-infection. Transgenic animals lacking complement component 3 (C3) were protected from SARS-CoV-induced weight loss, had reduced pathology (inflammatory cells in the large airway and parenchyma, perivascular cuffing, thickening of the interstitial membrane, and low levels of intra-alveolar edema), had improved respiratory function, and exhibited lower levels of inflammatory cytokines or chemokines in the lung and periphery. Notably, the kinetics of viral replication were unaltered in the C3-deficient mice relative to wildtype controls, suggesting that the observed effects were due to control of complement-mediated inflammatory processes and not reduction of viral titer. Complement protein 3 is a central hub in the complement cascade and acts as a relay for activation from the alternative pathway. However transgenic mice lacking alternative pathway proteins Factor B or C4 did not have the same protection from CoV-mediated weight loss as compared with C3-deficient mice, suggesting that inhibition of the complement alternative pathway alone is insufficient. This implies that inhibition of a key relay point such as C3 or potentially C5, may be required.

A second model of viral-mediated lung infection also points to a role for complement (Jiang, 2018). A MERS-CoV infection in mice causes severe acute respiratory failure and high mortality accompanied by elevated secretion of cytokines and chemokines. In these infected mice, excessive complement activation was detected. Increased concentrations of C5a and terminal complement complex (C5b-9), activation products resulting from cleavage of C5, were detected in sera and lung tissue, respectively. Blocking C5a with a specific antibody to the C5a receptor (C5aR) reduced alveolar macrophage infiltration and interferon (IFN)-gamma receptor expression in lung, resulting in less tissue damage. Decreased spleen tissue damage was also observed. Interestingly, anti-C5aR treatment led to decreased viral replication in lung tissues.

Patients infected by avian influenza virus H5N1 can also present with severe pneumonia, acute lung injury, or ARDS. The histopathological changes in the lungs are like those observed in severe acute respiratory syndrome (SARS) (Ng, 2006). In a mouse model of H5N1, complement activates immune effector cells and drives lung inflammation. Complement proteins C3a and C5a can increase vascular permeability, recruit and activate leukocytes, activate endothelial cells, upregulate adhesion molecule and cytokine expression, and induce goblet cell secretion of mucus, exacerbating disease through multiple mechanisms. In these mice, deposition of C3, C5b-9, and mannose-binding lectin (MBL)-C was observed in lung tissue. Upregulation of MBL-associated serine protease-2 (MASP-2) and complement receptors C3aR and C5aR was

also detected. Specific inhibition of either C3aR or C5a in the infected mice was effective in reducing lung damage, attenuating inflammation and neutrophil infiltration in the lung, and improving survival (Sun, 2013).

